5.53 Compensation

The patients will receive no compensation for their participation.

5.6 ADVERSE REACTION AND THEIR MANAGEMENT

A potential area of concern is that there may not be continuous communication among patients, DFCI transplant providers, and local providers. For this reason we have created the ACT.md web tool for providers to communicate with each other in real time and for patients to directly observe – and potentially add to – this communication (see section 5.52).

The non-randomized cohort of patients will receive Usual Care following their HCT procedure. They will be subject to the same medical record reviews and surveys in the Usual Care arm.

The consent forms outline the risks associated with participation. The risks to both the randomized and non randomized cohorts are expected to be minimal and all attempts will be made to minimize any anticipated issues with communication. If a patient declines

Version 8 , 11/16/2020

randomization and collection of outcomes, then the patient declines complete participation, s/he will not sign informed consent, will not be in this research study and no data will be collected.

The coordinating center (Dana-Farber) will take several steps to protect against and to minimize risks to privacy of individuals and confidentiality of data:

1. All data analyses will be conducted at Dana-Farber under the direct supervision of the PI.
2. Once the data are received, all study data will be stored on a password-protected RedCap database.

Data will be used for research purposes only. At no time will any patient be individually identified in the final analyses. We are confident that the steps outlined above will effectively protect against this risk.

Estimated study population characteristics are presented in Table 3, which are derived from our recent survey of patients at 180 days after HCT (in the table, autologous patients are excluded).^{4,11,12} The response rate we achieved (72%) provides insight into the high level of engagement of HCT patients and caregivers, even when concerning difficult topics such as personal finances.

Finally, to address study risk of missed tasks and miscommunication, we have planned interim analyses to determine if there are worse HCT-related outcomes for Shared Care patients; if so, the study will be stopped immediately and patients returned to usual care.

5.61 Reporting Adverse or Unanticipated Events

Any unanticipated event will be reported to the IRB and the DSMB. Interim analyses will help determine if there are worse HCT-related outcomes for Shared Care patients; if so, the study will be stopped immediately and patients returned to usual care

6.1 GENERAL DESCRIPTION AND CHARACTERISTICS OF DFCI HCT PATIENT POPULATION

Estimated study population characteristics are presented in Table 3, which are derived from our recent survey of patients at 180 days after HCT (in the table, autologous patients are excluded).^{4,11,12} More detail about PROs, handling of missing data, and heterogeneity of effects are detailed below.

Table 2. Shared Care Participating Sites and Number of Allogeneic HCT Patients in 2014 and 2015; Estimates for Accrual Per Year			
Proposed Shared Care Sites	State	Mean DFCI Allo HCT 2014 & 2015	If 80% agree to RCT/year
Stamford Hospital	CT	27	21
Dartmouth-Hitchcock	NH/VT	25	20
New York Oncology Hematology	NY	26	20
New England Cancer Specialists	S. ME	17	14
Eastern Maine Medical Center	N. ME	17	14
DFCI CCC/Satellites	MA	25	20
Total		136	108

6.2 PATIENT-REPORTED OUTCOMES (POWERED ON FACT-BMT)

Our primary hypothesis is that patients in the Shared Care group will have improved PROs compared to those in Usual Care due to a decreased burden of traveling and/or relocation to the HCT center. To investigate this hypothesis, the primary endpoint of this aim is powered by an expected improvement in FACT-BMT score between Shared Care to Usual Care 180 days post HCT. Of the total 324 patients who are randomized at study entry, we project that 80% will be alive at six months after allogeneic HCT and 70% will participate in the day 180 PRO assessment. These projections are based on survival data of DFCI HCT patients between 2012 and 2015, and the response rate from our prior survey regarding financial hardship experienced at 180 days after HCT described above (DFCI RR=72%; Table 5). This yields a sample size of 180. In a previous study of QOL for patients after allogeneic HCT, the mean FACT-BMT score at 100 days after HCT was 110 (± 20).¹⁹ Therefore, we believe a difference of 20 or more will be meaningful to show improved PROs at a similar time period (day 180). Extrapolating from this information, if the FACT-BMT score is 120 for Shared Care and 100 for Usual Care at 180 days post-HCT, there will be >99% power to detect this difference. If, however, the difference is 10, then there will be 90% power to detect this difference. This power calculation is based on asymptotic power of the Wilcoxon-Rank-Sum test against an alternative shift at the two sided significance level of 0.05, assuming the standard deviation of the difference is 20. An additional preliminary endpoint is expected difference in mean PSS-4, one of the potential quality of life surveys, score at day 180 post-HCT. In our financial hardship survey, the mean PSS-4 score for DFCI allogeneic patients (n=139) was 5.6 (± 3.2). Extrapolating from these data, if the difference in PSS-4 between the Shared and Usual Care groups is 2 with standard deviation 3.2, there will be 98% power to detect this difference at the two-sided significance level of 0.05.

Table 3. Sample DFCI Allogeneic HCT Patient Characteristics (n=139)

Patient Characteristics	%*
Diagnosis	
Acute Myeloid Leukemia	35
Myelodysplastic Syndromes (MDS)	20
Myeloproliferative Neoplasms	15
Acute Lymphoblastic Leukemia	15
Other	15
Sex	
Female	41
Male	59
Age	
60 or under	50
Over 60	50
Race	
White	96
Non-white	4
Insurance Type	
Employer sponsored	64
Government sponsored	29
Self-insured	7
Employment Status	
Employed	49
Unemployed	4
Not in the labor force (e.g., retired)	48
Marital Status	
Married	73
Not married	27
Education	
BA/Graduate Degree	49
No BA/Graduate Degree	51
Monthly Income	
Low income (< \$3,000)	28
Middle income (\$3,000 to \$6,999)	45
High income (>\$7,000)	27
*All categories do not equal 100% due to rounding	

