2.0 OBJECTIVES

This study will assess the effectiveness of a shared approach to post-HCT care to Usual Care (all care at DFCI) with respect to highly-relevant PROs and traditional HCT outcomes. We aim to:

1. Compare highly-relevant PROs for Shared versus Usual Care at 180 days post-HCT.
2. Compare 100-day non-relapse mortality (NRM) for patients in Shared Care versus Usual Care.

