5.5 DESCRIPTION OF STUDY PROCESS

This study of the effectiveness of the Shared Care method will be conducted with a randomized control trial comparing Shared Care and Usual Care. There will be 324 participants. Please see the protocol schema for the study time line. To review:

[figure not shown]
Pre-Transplant:

1. Recruit participants. Patient sign informed consent on day of overall HCT consent.
2. Patients randomized to one of two arms of the study.

Transplant:

Month 1: Patients admitted to DFCI or BWH for transplant. Receive stem cells.

1. Patients receiving full intensity allogeneic HCT will remain at the hospital for approximately 30 days.

Version 8 , 11/16/2020

2. Patients receiving a reduced intensity chemotherapy (RIC) HCT will be discharged approximately 1-2 days post-transplant. However, they will remain in Boston to attend frequent clinic visits until engraftment (10-12 days post-transplant).

Post-HCT: Full Intensity

Start of Shared Care: Patients will be discharged from hospital. Usual Care patients return to DFCI for all scheduled appointments through 180 days. Shared Care patients adhere to the following schedule:

1. For the first 90 days post-transplant, patients will alternate between local oncologist and DFCI for weekly visits.
2. From 90 to 180 days post-transplant, patients will alternate between local and DFCI every 2-3 weeks.

Post-HCT: Reduced-Intensity

Start of Shared Care: After evidence of engraftment at follow-up DFCI patient visits (ANC >500). Usual Care patients return to DFCI for all scheduled appointments through 180 days. Shared Care patients adhere to the following schedule:

1. For the first 90 days post-transplant, patients will alternate between local oncologist and DFCI for weekly visits.
2. From 90 to 180 days post-transplant, patients will alternate between local and DFCI every 2-3 weeks.

For patients who have not already established care with their designated local oncology team, a visit will be scheduled with that provider before HCT admission. An example of a Full Allo Shared Care patient's potential schedule is provided in Appendix K.

Premature termination of Shared Care:

Patients who relapse or require a second transplant will remain on protocol for QOL assessment but will no longer share care as part of the protocol.

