5.51 Instrument Administration

In addition to the standard data collection that is required for all patients who undergo HCT in the United States (CIBMTR)—including NRM and overall survival (OS)—all patients will be asked to complete PROs at 100 days and 180 days post-transplant, including any patients that prematurely terminate Shared Care for any reason. This was determined based on recommendations made by the modified Delphi panel of patients from a previous study (17-088). PROs will focus on assessing physical, social, and emotional wellbeing.

Version 8 , 11/16/2020

To understand the care that is received by individuals who choose not to be randomized, for those who consent, the study will track in parallel fashion their HCT-related outcomes and PROs. This will provide a non-randomized observational cohort which will be a second source of analysis and will also allow us to determine if there is a participation bias for those randomized. Given exuberant non-randomized (NR) enrollment and since NR participants are not included in our main analysis, we will cap the number of participants enrolled in the non-randomized arm at 1 patient per month. This will further lessen the burden of data collection with our limited resources and will allow us to better utilize the time of our research assistant involved in data collection. Patients declining randomization will receive usual care following HCT at Dana-Farber.

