approaches to handling missing data from dropouts. First, to assure PRO scores for non-responders are missing at random, we will perform a sensitivity analysis comparing the patient, HCT characteristics, and clinical outcomes between responders and non-responders. Second, we will perform multiple imputation on the outcome variable (including all independent variables) and compare the result without multiple imputation (i.e., inclusion of responding patients only). More importantly, with voluntary patient consent to participate in the study and proactive collection of survey data by the research team, we anticipate that the non-compliance rate will be minimal (<5%). Moreover, we anticipate that there will be no missing independent variables in all HCT patient-related data as this data must be reported to the CIBMTR database by the DFCI/BWH HCT center. Finally, to assure the robustness of our results, we will compare the FACT-BMT scores of the randomized Usual Care cohort with the non-randomized usual care cohort.

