- About half
- More than half
- All

Current Household Finances

17. In general, how satisfied are you with your family’s present financial situation? Please circle one.

Not satisfied at all Completely satisfied

1 2 3 4 5

18. How difficult is it for you/your family to meet monthly payments on your bills? Please circle one.

Not difficult at all Extremely difficult

1 2 3 4 5

19. How do your family’s finances usually work out at the end of the month?

Version 8 , 11/16/2020

- Some money left over
- Just enough money
- Not enough money

20. Compared to before your transplant, how has your monthly household income changed?

- It has decreased
- It is about the same
- It has increased

21. The following questions ask about things people do when money is tight. Since your transplant, how often did you or your family have to do any of the following? Please circle one.

	Never	Rarely	Sometimes	Often
Reduce spending on essential household expenses (food, clothing, rent/mortgage)?.....	1	2	3	4
Withdraw from retirement or savings accounts?...	1	2	3	4
Borrow money to help pay for bills?.....	1	2	3	4
Reduce leisure activities?.....	1	2	3	4
Cut back on prescribed medications?.....	1	2	3	4

22. Since your transplant, have you received any of the following resources to help cover expenses? Please check all that apply.

- Social Security Disability Insurance or Social Security Insurance
- Government assistance programs (food stamps, fuel or cash assistance)
- Dana-Farber financial assistance (discount hotel rooms, gas or food gift cards)
- Local or national charities (churches/synagogues, American Cancer Society)
- None of the above

23. What is your current monthly household income (include income from all household members)?

- Less than \$1,000
- \$1,000 to \$2,999
- \$3,000 to \$4,999
- \$5,000 to \$6,999
- \$7,000 or more

Health Insurance and Medical Costs

24. How satisfied are you with your current insurance coverage? Please circle one.

Not satisfied at All

Completely satisfied

1 2 3 4 5

25. About how much of your own money did you spend last month for your medical care (including prescriptions, co-payments, deductibles, and premiums)?

\$ _____ dollars per month

26. The next questions are about costs associated with your transplant that are not direct medical costs. Since your transplant, how difficult has it been for you to pay for the following costs? Please circle one number or “N/A” if you did not have the type of cost after your transplant.

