29. How would you rate your overall health during the past week?
 Very poor 1 2 3 4 5 6 7 Excellent

30. How would you rate your overall quality of life during the past week?
 Very poor 1 2 3 4 5 6 7 Excellent

E. FACT-BMT

FACT-BMT (Version 4)

Below is a list of statements that other people with your illness have said are important. Please circle or mark one number per line to indicate your response as it applies to the past 7 days.

PHYSICAL WELL-BEING		Not at all	A little bit	Some- what	Quite a bit	Very much
GP1	I have a lack of energy	0	1	2	3	4
GP2	I have nausea	0	1	2	3	4
GP3	Because of my physical condition, I have trouble meeting the needs of my family	0	1	2	3	4
GP4	I have pain	0	1	2	3	4
GP5	I am bothered by side effects of treatment	0	1	2	3	4
GP6	I feel ill	0	1	2	3	4
GP7	I am forced to spend time in bed	0	1	2	3	4

SOCIAL/FAMILY WELL-BEING		Not at all	A little bit	Some- what	Quite a bit	Very much
G81	I feel close to my friends	0	1	2	3	4
G82	I get emotional support from my family	0	1	2	3	4
G83	I get support from my friends	0	1	2	3	4
G84	My family has accepted my illness	0	1	2	3	4
G85	I am satisfied with family communication about my illness	0	1	2	3	4
G86	I feel close to my partner (or the person who is my main support)	0	1	2	3	4
Q1	Regardless of your current level of sexual activity, please answer the following question. If you prefer not to answer it, please mark this box  and go to the next section.					
G87	I am satisfied with my sex life	0	1	2	3	4

Please circle or mark one number per line to indicate your response as it applies to the past 7 days.

EMOTIONAL WELL-BEING

		Not at all	A little bit	Some-what	Quite a bit	Very much
GE1	I feel sad	0	1	2	3	4
GE2	I am satisfied with how I am coping with my illness	0	1	2	3	4
GE3	I am losing hope in the fight against my illness	0	1	2	3	4
GE4	I feel nervous	0	1	2	3	4
GE5	I worry about dying	0	1	2	3	4
GE6	I worry that my condition will get worse	0	1	2	3	4

FUNCTIONAL WELL-BEING

		Not at all	A little bit	Some-what	Quite a bit	Very much
GF1	I am able to work (include work at home)	0	1	2	3	4
GF2	My work (include work at home) is fulfilling	0	1	2	3	4
GF3	I am able to enjoy life	0	1	2	3	4

GF4	I have accepted my illness	0	1	2	3	4
GF5	I am sleeping well	0	1	2	3	4
GF6	I am enjoying the things I usually do for fun	0	1	2	3	4
GF7	I am content with the quality of my life right now	0	1	2	3	4

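### The day-100 FACT-BMT score is collected from everyone, but it has no stated analysis and is left out of the imputation of missing day-180 scores

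*Combined protocol and SAP*

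**What the plan says.** **Endpoint.** Objective 1 (section 2.0) is to "Compare highly-relevant PROs for Shared versus Usual Care at 180 days post-HCT". Section 6.2 powers this aim on an "expected improvement in FACT-BMT score between Shared Care to Usual Care 180 days post HCT", with a Wilcoxon rank-sum test.

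**Collection.** Section 5.51 states that "all patients will be asked to complete PROs at 100 days and 180 days post-transplant". Section 5.4 lists FACT-BMT among the four surveys and has them completed at DFCI visits.

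**Other FACT-BMT analyses.** Section 6.5 plans a regression of FACT-BMT on type of care and the Table 4 attributes. Section 6.3 compares the randomized and non-randomized Usual Care cohorts. Neither gives a day. Day 180 is therefore the only dated between-arm comparison, and no analysis is assigned to the day-100 score.

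**Missing scores.** Section 6.3 says "we will perform multiple imputation on the outcome variable (including all independent variables" and sets the result beside the responder-only result. The same section separates independent variables from outcome variables. It also says that the roughly 30% who do not agree to the PRO assessment are not counted as missing, and it expects non-compliance below 5%.

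**The concern.** A patient who completes FACT-BMT at day 100 and then misses day 180 has left a direct measurement of the same outcome about 80 days earlier. It is likely to predict the missing value better than age, donor type or graft source. An imputation model that lacks it treats a patient who was doing badly at day 100 like one with the same transplant characteristics who was doing well.

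The check of responders against non-responders in section 6.3 covers patient and transplant characteristics and clinical outcomes. It does not mention earlier PRO scores, so it would not show this either.

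The set of patients to be imputed is a second gap. If the roughly 30% are not regarded as missing, the imputation reaches only the few percent classed as dropouts, and most survivors without a score stay outside it.

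**Working it through.** **1. The plan's own figures.** Evaluable patients: 324 × 0.80 × 0.70 = 181.4, against the stated 180 (90 per arm). Wilcoxon power for 10 points with SD 20: effective n = 90 × 3/π = 85.9 per arm; z = 10 / (20 × √(2/85.9)) = 3.28; power = Φ(3.28 − 1.96) = 90.6%, against the stated 90%. Both reproduce, so the power statement is not in question.

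**2. Survivors without a day-180 score.** Per arm: 162 × 0.80 ≈ 130 alive, less 90 responders, leaves about 40.

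**3. How many have a day-100 score.** The documents do not say. Assume 30-70% of the 40, so m = 12 to 28 per arm.

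**4. Precision.** Relative to responders only, and assuming that all responders also have a day-100 score, the standard-error ratio is √(1 − ρ² × m/(n + m)), with n = 90 and an assumed correlation ρ of 0.5-0.7.

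| Case | ρ | m | m/(n + m) | SE ratio | Reduction |
|---|---|---|---|---|---|
| Low | 0.5 | 12 | 0.118 | 0.985 | 1.5% |
| High | 0.7 | 28 | 0.237 | 0.940 | 6.0% |

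The standard error of the arm difference is 20 × √(2/90) = 2.98 points. It would fall to between 2.94 and 2.80.

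**5. Bias in one arm's mean.** Let p be the share of survivors who have day 100 but lack day 180: 12/130 = 0.092 to 28/130 = 0.215. Let g be how much lower they scored at day 100, assumed 5-10 points. With equal SDs, and missingness that depends only on the day-100 score, the shift in the responder-only mean that the day-100 score can correct is p × ρ × g:
- low: 0.092 × 0.5 × 5 = 0.23 points
- high: 0.215 × 0.7 × 10 = 1.5 points

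The arm contrast is affected only by the difference between the arms in this product. If both arms have the same p and g, it is zero.

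**6. Does timing separate day 180 from day 100?** The comparison uses Appendix K and assumes that Usual Care keeps the same calendar with every visit at DFCI.

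| | Near day 100 | Near day 180 |
|---|---|---|
| Example visits | local 86, none 93, DFCI 100 | local 170, none 177, DFCI 184 |
| DFCI trips in the 7-day recall, each arm | 1 | 1 |
| Cumulative DFCI trips, Usual vs Shared | 8 vs 4 | 14 vs 7 |

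The recall week is the same at both times, and the cumulative gap is larger at day 184.

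**The case against.** **Day 180 is a reasonable primary time, and the plan does not rely on imputation alone.** Both statements stand. Section 5.4 says the intervention lasts 180 days, and the imputed result is set beside the responder-only result. Section 6.3 does not rule out the day-100 score; it fails to name it, and its wording points the other way. Many who decline the PRO assessment may have no day-100 score at all, which is why the gain is small.

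**A reader might infer that day 180 is the wrong time.** Section 6.2 expects the benefit "due to a decreased burden of traveling and/or relocation to the HCT center", and section 5.5 says "From 90 to 180 days post-transplant, patients will alternate between local and DFCI every 2-3 weeks" after weekly visits before that. FACT-BMT asks patients to "indicate your response as it applies to the past 7 days". The rate of trips saved does fall after day 90. But day 100 also lies after day 90 and has the same one-trip recall week in the Appendix K example. The two-to-one ratio of DFCI visits continues, and the cumulative gap is largest at the end. The survey at about 180 days described in section 1.2 found travel-related costs associated with financial hardship, and hardship with worse quality of life. The documents do not show that day 180 is the worst time or that a null result could not be interpreted.

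**A reader might also infer that the travel-cost question is ignored.** Item 26 of the Financial Assessment asks: "Since your transplant, how difficult has it been for you to pay for the following costs". Objective 1 covers PROs at day 180 in general, so what is missing is a named score or test. Its not-applicable option is a further obstacle. Shared Care may change who incurs a relocation cost, so comparing only those who answer would condition on something that happens after randomization.

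**Conclusion.** The concern holds in a narrow form. The day-100 FACT-BMT has no stated analysis, and the imputation of day 180 as described omits it, although about 30% of survivors are projected not to respond.

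The size is modest: a 1.5-6% smaller standard error, and a correctable shift of about 0.2-1.5 points in one arm's mean, against the 10-point difference that has 90% power. These ranges rest on assumed values for day-100 availability (30-70% of non-responders), correlation (0.5-0.7) and day-100 gap (5-10 points). They are measured against the responder-only analysis, so the gain over imputation with good baseline predictors would be smaller. The contrast benefits only if non-response differs by arm and is related to the day-100 score.

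The choice of day 180 and the stated power are not in error. Separately, section 5.5 has weekly visits to day 90, whereas Appendix K moves to bi-weekly visits from day 59. These passages must be reconciled.

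**What to change.** Keep day-180 FACT-BMT as the primary PRO endpoint and change the analysis text as follows.

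1. In section 6.3, name the day-100 FACT-BMT score and randomized arm as predictors in the imputation model for day 180, alongside the variables already planned.
2. Apply it to every randomized patient alive at day 180 without a score, including those whom section 6.3 does not regard as missing.
3. As an alternative to items 1 and 2, estimate the day-180 contrast as a sensitivity analysis from a repeated-measures model of both assessments (arm, time, arm by time). Restrict it to patients alive at day 180, so that it does not implicitly impute scores after death.
4. Add the day-100 FACT-BMT score to the comparison of responders with non-responders.
5. Name the day-100 contrast between arms as a secondary result.
6. Reconcile the visit schedules in section 5.5 and Appendix K.

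The cost is SAP wording, a little more analysis and one more secondary comparison. No new data, visits or patients are needed.
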